8.10.2. Rationale

A total of 176 patients was chosen as the number of patients evaluable for risk factors related to the onset of VOD/SOS. The incidence of VOD/SOS was 12.3% (26/212 patients) in clinical studies (Studies B1931022 and B1931010).

A sample size enabling to evaluate the effect of risk factors related to the onset of VOD/SOS, which were identified in clinical studies, under actual conditions of use, and to search other risk factors was selected. Assuming the true incidence of 12.3% in all patients, a true relative risk associated with the onset of events in subgroups of 3.0 (equivalent to the incidence in the high and low risk groups being assumed to be 18.5% and 6.2%, respectively), and a ratio of the patients in each group being 1:1, when defining a probability of detecting a statistically significant relative risk as power, a sample size of 176 patients would provide power of 80.4% in a (two-sided) chi square test with a significance level of 0.1.

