- Best overall response and MRD [CR/CRi achieved and negativity achieved, CR/CRi achieved and negativity not achieved, progression/relapse and negativity achieved, progression/relapse and negativity not achieved] \* "Indeterminate/other" and "not performed" are excluded.

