#### 8.1.3. Binary variables

For binary variables, patients falling into each binary category will be summarized in terms of frequency (n) and proportion. If a confidence interval (CI) is determined for a proportion, the two-sided 95% CI will be determined using the exact method.

For a comparison of proportion between subgroups, the risk ratio (RR) and its 95% CI will be determined. In addition, the RRs and their 95% CIs will be graphically presented.

For statistical tests, Fisher's exact test will be performed to test correlations in nominal scale data, and Cochran-Armitage test (exact method) to test correlations in ordinal scale data. If, however, it is difficult to use the exact method, chi-square test or Cochran-Armitage test with normal approximation will be used as an alternative to the exact method.

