**Exploration of factors associated with the occurrence of VOD/SOS (subgroup analyses):** Patients who experienced VOD/SOS after the start of this drug and patients who experienced VOD/SOS with HSCT performed after the start of this drug will be summarized in terms of n and proportion by each of the following factors selected from those specified in Section 5.4. In addition, risk ratios for the proportion of patients with the AR for different subgroups will be determined as per Section 8.1.3 and presented graphically. If, however, there is a category with less than 10 patients and after reconsideration it is considered difficult to determine the risk ratio for the category, it will not be determined for the relevant category. To investigate correlation between factors and occurrence of the ADR, statistical tests specified in Section 8.1.3 will be performed.

- Age [ $< 15$  years,  $\geq 15$  to  $< 65$  years,  $\geq 65$  years]
- Age [ $< 18$  years,  $\geq 18$  to  $< 55$  years,  $\geq 55$  years]
- Age [ $< 15$  years,  $\geq 15$  to  $< 40$  years,  $\geq 40$  years]
- Hepatic impairment
- Medical history (past) - VOD/SOS
- Medical history (past) - Hepatitis or hepatic disease
- Medical history (present) - VOD/SOS
- Medical history (present) - Hepatitis or hepatic disease
- ECOG PS before the start of this drug [ $0, 1, \geq 2$ , not performed]
- AST and ALT levels immediately before the start of this drug
- $\gamma$ -GTP level immediately before the start of this drug
- Total bilirubin level immediately before the start of this drug
- Platelet count immediately before the start of this drug
- Peripheral blast count immediately before the start of this drug
- Salvage line of the induction treatment with this drug
- HSCT before the start of this drug
- HSCT after the start of this drug

Similarly, VOD/SOS that occurred with HSCT performed after the start of this drug will be analyzed with respect to the following factors:

- Type of the first HSCT after the start of this drug
- Donor of the first HSCT after the start of this drug
- Conditioning with alkylating agent for the first HSCT after the start of this drug
- Conditioning with busulfan for the first HSCT after the start of this drug

- ECOG PS before conditioning for the first HSCT after the start of this drug [0, 1, ≥ 2, not performed]
- AST and ALT levels before conditioning for the first HSCT after the start of this drug

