Patients with early death after HSCT will be summarized in terms of n and proportion by each of the following factors selected from those specified in Section 5.4. In addition, risk ratios for the proportion of patients who died for different subgroups will be determined as per Section 8.1.3 and presented graphically. If, however, there is a category with less than 10 patients and after reconsideration it is considered difficult to determine the risk ratio for the category, it will not be determined for the relevant category. To investigate correlation between factors and death, statistical tests specified in Section 8.1.3 will be performed. Similar analyses will also be performed for early transplant-related death after HSCT (non-relapse death).

- Age [< 15 years, > 15 to < 65 years, ≥ 65 years]
- Age [< 18 years, ≥ 18 to < 55 years, ≥ 55 years]
- Age [< 15 years, ≥ 15 to < 40 years, ≥ 40 years]
- Disease name
- Chromosome karyotype [normal, t (4;11)]
- Chromosome karyotype [Philadelphia chromosome positive, negative] \* Philadelphia chromosome is considered positive if the chromosome karyotype is t(9;22).
- Hepatic impairment
- Medical history (past) - VOD/SOS
- Medical history (past) - GVHD
- Medical history (past) - Hepatitis or hepatic disease
- Medical history (present) - VOD/SOS
- Medical history (present) - GVHD
- Medical history (present) - Hepatitis or hepatic disease
- ECOG PS before the start of this drug [0, 1, ≥ 2, not performed]
- Hemoglobin level immediately before the start of this drug
- Platelet count immediately before the start of this drug
- Peripheral blast count immediately before the start of this drug

- Myeloblast count immediately before the start of this drug
- Salvage line of the induction treatment with this drug
- HSCT before the start of this drug
- Type of the first HSCT after the start of this drug
- Donor of the first HSCT after the start of this drug
- Conditioning with alkylating agent for the first HSCT after the start of this drug
- Conditioning with busulfan for the first HSCT after the start of this drug
- ECOG PS before conditioning for the first HSCT after the start of this drug [0, 1,  $\geq 2$ , not performed]
- Hemoglobin level before conditioning for the first HSCT after the start of this drug
- Platelet count before conditioning for the first HSCT after the start of this drug
- Peripheral blast count before conditioning for the first HSCT after the start of this drug

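### SAP 8.2.3 tests risk factors with 'not performed' (or 'unknown') as a level and no rule to remove it, so the p-value partly measures missing data

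*SAP*

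**What the plan says.** SAP 8.2.3.3 (early death after HSCT) lists "ECOG PS before the start of this drug [0, 1, ≥ 2, not performed" as a factor, and the pre-conditioning ECOG PS in the same form. Hemoglobin, platelets, peripheral blasts, myeloblasts, best response and MRD take their levels from SAP 5.4, where *not performed* is again a level. In SAP 8.2.3.1 (VOD/SOS) the same holds for AST/ALT, γ-GTP, bilirubin and others, and "statistical tests specified in Section 8.1.3 will be performed". SAP 8.2.3.4 repeats the pattern for ADRs.

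SAP 8.1.3 assigns Fisher's exact test to nominal data and the "Cochran-Armitage test (exact method) to test correlations in ordinal scale data". It gives no trend scores and does not mention *not performed*.

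Elsewhere the SAP does deal with such levels:
- SAP 5.4 lists karyotype with *unknown*. The SAP 8.2.3.3 list rewrites both karyotype factors without it, but rewrites ECOG PS with *not performed* kept.
- For the combined response-and-MRD factor, SAP 5.4 states that "Indeterminate/other' and 'not performed' are excluded".
- SAP 8.2.4.1 and 8.2.4.2 add a second analysis without unassessed patients.

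The rule for categories with fewer than 10 patients concerns the risk ratio only, not the test. SAP 4.1 treats all p-values as descriptive, with no set significance level, but allows a post-hoc threshold for screening.

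**The concern.** Risk factors for VOD/SOS and for early death after HSCT are a stated objective (Protocol 7.2 and 8.12.2.1), and these p-values are the screening aid for them. A patient with no recorded ECOG PS does not have a performance status worse than 2. A missing-data level placed after the ordered levels breaks the ordering a trend test needs. In a two-level comparison it adds a third column, which can make the p-value small without any difference between the two real levels.

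The data come from routine charts, and Protocol 8.14 expects missing information, so the level is unlikely to be empty. Because the plan does not settle the point, two programmers could follow it and report different p-values.

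**Working it through.** **1. The plan's own figure.** Protocol 8.10.2 states that "a sample size of 176 patients would provide power of 80.4% in a (two-sided) chi square test with a significance level of 0.1", with "a ratio of the patients in each group being 1:1". Using n = 88 per group, p1 = 0.1845, p2 = 0.0615, mean 0.123:

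- Null SE = √(2 × 0.123 × 0.877 / 88) = 0.0495
- Alternative SE = √((0.1845 × 0.8155 + 0.0615 × 0.9385) / 88) = 0.0486
- Power = Φ((0.123 − 1.645 × 0.0495) / 0.0486) = Φ(0.854) = 80.4%

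The figure reproduces (80.2% with the rounded 18.5% and 6.2%). It assumes two groups and no missing-data group.

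**2. Assumptions not in the documents.** 10% not performed (18 of 176); ECOG PS groups of 62/62/34; VOD/SOS risks of 6/12/24% for ECOG PS 0, 1, ≥ 2; level 0.10; equally spaced scores, with *not performed* scored 3 when kept.

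**3. Trend test, by hand.** T = Σ s·x − p̄·Σ n·s and V = p̄(1 − p̄)[Σ n·s² − (Σ n·s)²/N]. Power is approximately Φ(T/√V − 1.645), with expected counts put in.

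- Dropped (N = 158): T = 23.76 − 15.90 = 7.86; V = 0.1073 × 91.04 = 9.77; z = 2.52; power about 81%.
- Kept, not-performed risk 12% (N = 176): T = 30.24 − 22.46 = 7.78; V = 0.1072 × 167.64 = 17.96; z = 1.84; power about 58%.
- Kept, risk 6%: T = 27.00 − 21.33 = 5.67; V = 17.18; z = 1.37; power about 39%.
- Kept, risk 24%: T = 36.72 − 24.71 = 12.01; V = 19.49; z = 2.72; power about 86%.

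The extra level nearly doubles the score spread (91 to 168), and T rises to match only if the not-performed group has high risk.

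**4. Simulation of the same setting** (normal-approximation test):

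| Not-performed risk | Level kept | Level dropped |
|---|---|---|
| 6% | 37% | 82% |
| 12% | 57–58% | 82% |
| 24% | 85–86% | 82% |

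With only 4 patients not performed (67/67/38/4), power is about 73% (risk 6%) or 77% (risk 12%) kept, against 84% dropped.

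With the exact test, a shallower gradient (6.2/12.35/18.5%) and average risk in the missing group, Cochran-Armitage power kept versus dropped is 41% vs 58% (10% missing), 30% vs 53% (20%) and 20% vs 43% (30%). Treating the four levels as nominal under Fisher gives 48% at 10% missing. Three readings of one plan thus give 41%, 48% and 58%.

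**5. Two-level factor, exact Fisher** (79/79/18; 6.15% vs 18.45%). With not-performed risk at 6.15% or 12.3%, power is about 70% kept and 70% dropped. At 18.45% risk it is about 75% kept against 70% dropped.

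**6. False flags** (10% risk in every observed level, 30% in *not performed*, 10% missing, level 0.10).

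- Fisher, two-level: about 64–66% kept, 5–6% dropped.
- Trend test, ECOG PS: about 51% kept, 10–11% dropped. By hand, T = 29.20 − 22.16 = 7.04, V = 17.76, z = 1.67, Φ(0.025) = 51%. With 12.3% observed risk it is 41%.
- Equal risk in all levels: about 9–10% for both tests with the level kept, so the nominal rate holds.

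**7. The early-death population.** This is only HSCT recipients who finished the survey, and their number is not given. With an assumed 100 patients, 10% missing, three observed levels and exact tests:

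- A 10/20/30% gradient with average risk in the missing group gives trend power 43% kept, 58% dropped.
- 20% deaths in all observed levels and 40% in *not performed* gives false flags of 20–23% (trend) and 28–31% (Fisher) kept, against 7–9% dropped.

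**The case against.** The strongest reply is that the SAP never says *not performed* receives a trend score. SAP 8.1.3 reserves Cochran-Armitage for ordinal data, and a list ending in *not performed* is not ordinal, so a sensible programmer would drop the level or use Fisher. The lists also serve the frequency tables, where such a row is proper. This stands in part: scoring the level last is an inference. But the SAP removes comparable levels in writing elsewhere, including in the same list, so it cannot be assumed that the level is meant to drop out here.

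A reader might also infer more than the documents support:

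- **A general loss of power.** Most affected factors have two observed levels, and under the specified Fisher test their power is essentially unchanged. For ECOG PS the loss disappears when the unassessed patients have high risk.
- **A broken type I error rate.** False flagging requires missingness related to outcome. SAP 4.1 sets no significance level, so a flag here means a misleading screening p-value, not a failed confirmatory test. The counts and proportions printed beside it would partly reveal the cause.
- **Distorted risk ratios.** Each ratio is taken against a reference level, so a *not performed* row does not alter the ratio for any other level. It can be useful evidence that missingness is informative and need not be removed.

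**Conclusion.** The point holds for the tests, not for the tables or risk ratios. SAP 8.2.3.1, 8.2.3.3 and 8.2.3.4 test factors that carry *not performed* or *unknown* with no exclusion rule.

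For ordered factors, mainly ECOG PS, the literal trend test has no valid ordering. Its power at 176 patients and 10% missing is about 37–58% instead of 82% when the missing group has low or average risk; with only 4 patients missing the loss is about 7 to 11 points. For two-level factors the harm is false flagging under outcome-related missingness, not power.

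The missing share, the ECOG PS distribution, the risk in unassessed patients and the number of HSCT recipients are assumptions, so the sizes are illustrative. That the plan leaves the tested levels unsettled does not depend on them.

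**What to change.** Add to SAP 8.1.3: *Patients in the levels not performed or unknown are shown in the tables (with their category risk ratio where estimable) but are excluded from the statistical tests and trend scores; the number excluded is reported for each factor.*

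This extends to all tested factors what the SAP already does for karyotype in 8.2.3.3 and for response-and-MRD in 5.4. It needs no new data and leaves the tabulations unchanged. The cost is slightly fewer patients in each test. The reported number excluded, with the row kept in the table, lets a reader judge whether missingness itself is related to outcome.

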8.8.3. Targeted Drug Use Record (Actual Treatment Record)

- (1) Date of dosing
- (2) Single dose
- (3) Number of cycles administered

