8.8.11. Clinical Evaluation

8.8.11.1. Hematologic Remission

Response will be assessed according to the following response criteria, and the best overall response during the observation period will be entered. However, if subsequent treatment for the target disease is started or HSCT is performed, the best overall response before the start of the subsequent treatment or HSCT, whichever is earlier, will be entered.

Response criteria

1. CR
 - No peripheral blasts or extramedullary disease (no lymphadenopathy, splenomegaly, or skin/gum infiltration/testicular mass/CNS involvement)
 - Trilineage hematopoiesis (TLH) and <5% blasts
 - Absolute neutrophil count (ANC) >1,000/ μ L
 - Platelets >100,000/ μ L
 - No recurrence for 4 weeks
2. CRi (CR with incomplete count recovery)
 - Recovery of platelets but <100,000/ μ L or ANC is <1,000/ μ L
3. Progressive disease (PD)
 - Increase of at least 25% in the absolute number of peripheral blood or bone marrow blasts or development of extramedullary disease
4. Relapsed disease
 - Reappearance of blasts in the blood or bone marrow (>5%) or in any extramedullary site after CR
5. Inevaluable

Inotuzumab

B1931024 NON-INTERVENTIONAL STUDY PROTOCOL

Amended 8, 12 December 2023

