## 2.1. Study Design

- **Target population**

*All patients who received this drug will be included in this survey.*

- **Survey period**

*The scheduled periods of this survey are as follows:*

*Survey period: From the date of launch of this drug to 5 years\**

*Registration period: From the date of launch of this drug to the time of lifting of approval conditions for all-case survey\**

*\*: Patients who started to receive this drug on or after May 1, 2020 will only be registered.*

The protocol may be changed to terminate the registration only period, but this change will not affect the SAP.

- **Observation period**

*Observation period: The observation period is to be 52 weeks for patients who did not undergo hematopoietic stem cell transplant (HSCT) within 52 weeks after the start of the treatment with this drug and up to 52 weeks after HSCT for patients who underwent HSCT within 52 weeks after the start of this drug. If patients who started to receive this drug on or before April 30, 2020 are transferred to another hospital during the observation period, the transferred hospitals will be requested to conclude a contract for the conduct of this survey, and the information at the transferred hospitals will be collected as much as possible.*

*[1] Treatment Period*

*From the start of treatment to Day 28 post-final dose: For assessments of safety (e.g., adverse events) and effectiveness (hematologic response, survival time)*

*[2] Follow-up period*

*For 52 weeks from 29 days after the final dose (for patients who did not undergo HSCT by 52 weeks after the start of treatment) or for 52 weeks after HSCT (for patients who underwent HSCT by 52 weeks after the start of treatment): For assessments of safety (VOD/SOS) and effectiveness (survival time)*

The starting point for the 52 week follow-up after HSCT is the day of the last HSCT performed within 52 weeks after the start of this drug.

- **Safety specification**

See Protocol Section 7.1.

- **Sample size and its rationale**

*Of the patients who have received this drug, a total of 176 patients with relapsed or refractory CD22 positive (CD22+) acute lymphocytic leukemia (ALL) will be included in the safety analysis set. In consideration of dropouts during the survey, 200 patients will be registered.*

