- Peripheral blast count before conditioning for the first HSCT after the start of this drug [≤ 1000 /µL, > 1000 /µL, not performed]
- Myeloblast count before conditioning for the first HSCT after the start of this drug [≤ 50%, > 50%, not performed]
- Time from the date of final dose of this drug to the date of the first HSCT after the start of this drug [< 4 weeks, ≥ 4 weeks to < 8 weeks, ≥ 8 weeks to < 12 weeks, ≥ 12 weeks to < 16 weeks, ≥ 16 weeks]
- Treatment cycles [1 cycle, 2 cycles, 3 cycles, 4 cycles, 5 cycles, 6 cycles, > 6 cycles]
- Treatment cycles [≤ 3 cycles, ≥ 4 cycles]
- Dosing of > 1.8 mg/m^2 per cycle [absent, present] (Considered to be present, if there is a cycle of > 1.8 mg/m^2 per cycle during the treatment period.)
- Pregnancy [absent, present] \* Pregnancy during the treatment period. Limited to cases in which information on pregnancy is collected
- Best overall response [complete remission (CR) or complete remission with incomplete hematologic recovery (CRI), progression or relapse, indeterminate/other, not performed]
- Minimal residual disease (MRD) [negativity achieved, negativity not achieved, test not performed]
  - \* Irrespective of the result of best overall response.
- Best overall response and MRD [CR/CRI achieved and negativity achieved, CR/CRI achieved and negativity not achieved, progression/relapse and negativity achieved, progression/relapse and negativity not achieved] \* "Indeterminate/other" and "not performed" are excluded.
- Adverse drug reactions that occurred during the treatment period - liver disorder as a safety specification [absent, present]

Subgroup analyses of hematologic response and MRD will be performed for the following patient characteristics and other factors:

- Age [< 15 years, ≥ 15 to < 65 years, ≥ 65 years]
- Age [< 18 years, ≥ 18 to < 55 years, ≥ 55 years]
- Age [< 15 years, ≥ 15 to < 40 years, ≥ 40 years]
- Disease name [Relapsed CD22+ acute lymphocytic leukemia (ALL), refractory CD22+ ALL]
- Chromosome karyotype [normal, t (4;11), unknown]
- Chromosome karyotype [Philadelphia chromosome positive, negative, unknown]\* Philadelphia chromosome is considered positive if the chromosome karyotype is t(9;22).
- Hemoglobin level immediately before the start of this drug [< 10 g/dL, ≥ 10 g/dL, not performed]
- Platelet count immediately before the start of this drug [< 10 × 10^4/µL, ≥ 10 × 10^4/µL, not performed]

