## 6. ENDPOINTS AND COVARIATES

### 6.1. Safety Endpoints

- Adverse events: All undesirable or unintended signs or symptoms that occurred after administration of this drug, regardless of causal relationship
- Adverse drug reactions: Adverse events assessed as causally related to this drug by the physician

- Serious adverse events or serious adverse drug reactions: Adverse events or adverse drug reactions assessed as serious by the physician

- Death after HSCT:

- Time to death after HSCT: Days and weeks from the date of first HSCT after the start of this drug to the date of death
- Event: Death (for any cause)
- Censoring: The patient is confirmed alive at the time of completion or discontinuation of the survey. The endpoint will be censored on the day when patient's survival was last confirmed.

Early death after HSCT is defined as the above event that occurred within 100 days after the first HSCT after the start of this drug. Early death is supposed to be absent if the patient died on 101 days or later, or was confirmed alive at the time of completion/discontinuation of the survey.

- Transplant-related death after HSCT (non-relapse death):

- Time to transplant-related death after HSCT: Days and weeks from the date of first HSCT after the start of this drug to the date of death.
- Event: Death due to non-tumor-related causes, resulting from worsening of the target disease of this drug
- Competing risks: Death due to tumor-related causes, resulting from worsening of the target disease of this drug
- Censoring: The patient is confirmed alive at the time of completion or discontinuation of the survey. The endpoint will be censored on the day when patient's survival was last confirmed.

Early transplant-related death after HSCT (non-relapse death) is defined as the above event that occurred within 100 days after the first HSCT after the start of this drug. Early death is supposed to be absent if the patient died on 101 days or later, or was confirmed alive at the time of completion/discontinuation of the survey.

- Transplant-unrelated death after HSCT (relapse death):

- Time to transplant-unrelated death after HSCT: Days and weeks from the date of first HSCT after the start of this drug to the date of death.
- Event: Death due to tumor-related causes, resulting from worsening of the target disease of this drug
- Competing risks: Death due to non-tumor-related causes, resulting from worsening of the target disease of this drug

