- Myeloblast count before conditioning for the first HSCT after the start of this drug
- Time from the date of final dose of this drug to the date of the first HSCT after the start of this drug
- Treatment cycles [1 cycle, 2 cycles, 3 cycles, 4 cycles, 5 cycles, 6 cycles,  $> 6$  cycles]
- Treatment cycles [ $\leq 3$  cycles,  $\geq 4$  cycles]
- Best overall response
- MRD
- Best overall response and MRD
- Adverse drug reactions that occurred during the treatment period - liver disorder as a safety specification

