### 9. LISTINGS

The following data will be listed in tabular form:

- All patients
- Off-label diseases
- Dosing records
- Reasons for completion/discontinuation of treatment \* Only for "other" reasons.
- Concomitant anti-malignant tumor agents
- Hematopoietic stem cell transplants (before and after the start of this drug)
- Patients with AEs
- Patients with ADRs
- Patients with ADRs who were excluded from the safety analysis
- ADRs with data deleted
- Patients with serious ADRs
- Patients with serious AEs
- Patients with AEs of VOD/SOS
- Patients with ADRs in the population with hepatic impairment

- Patients with ADRs in the population with renal impairment
- Elderly patients with ADRs
- Patients with ADRs by event included in the safety specification
- Laboratory test values

The descriptions included in the listing of "Off-label diseases" are as follows:

- Disease name (as recorded by the physician)
- ADRs

The descriptions included in the listing of "Dosing records" are as follows:

- Items in the "Record of the Treatment with This Drug" page of the case report form
- Number of treatment cycles of this drug
- Number of doses and total dose of this drug in each cycle
- Total dose amount of this drug

The descriptions included in the listing of "Reasons for completion/discontinuation of treatment" are as follows:

- Details of the "other" reasons for the completion/discontinuation of treatment

The descriptions included in the listing of "Concomitant anti-malignant tumor agents" are as follows:

- Drug code
- Drug name [code-based name]
- Drug name [generic name]
- Drug name (product name) [as per physician's description]
- Start date

The descriptions included in the listing of "Hematopoietic stem cells transplants (before and after the start of this drug)" are as follows:

- Disease name (as per physician's description), salvage line number, and presence/absence of resumption of this drug
- Items in the "Hematopoietic Stem Cell Transplant (before the start of the treatment with this drug)" page of the case report form
- Items in the "Hematopoietic Stem Cell Transplant (treatment and follow-up periods)" page of the case report form. In addition, the following items will also be presented:
  - Months (days) from the start of this drug to the day of transplant
  - Months (days) from the date of the final dose of this drug to the day of transplant

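### The treatment-cycle factor for early death after HSCT is not limited to cycles before the transplant, so any dosing after HSCT would make high cycle counts look safer than they are

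*SAP*

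**What the plan says.** SAP 8.2.3.3 explores factors for early death after HSCT. Among them is "Treatment cycles [1 cycle, 2 cycles, 3 cycles, 4 cycles, 5 cycles, 6 cycles" and a top class above 6, followed by a two-class version (up to 3, 4 or more). SAP 5.4, where the factor is defined, attaches no time limit. The same factor is in the HSCT part of the VOD/SOS exploration in SAP 8.2.3.1.

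SAP 6.1 defines early death as death "within 100 days after the first HSCT after the start of this drug", so time zero is the transplant.

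The exposure side is not tied to that time zero. Protocol 8.8.3 collects dosing dates and "Number of cycles administered". SAP 2.1 defines the treatment period as "From the start of treatment to Day 28 post-final dose", so it closes relative to the final dose and not at HSCT. In SAP 9 the HSCT and VOD/SOS listings both carry "salvage line number, and presence/absence of resumption of this drug".

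**The concern.** A factor for an outcome counted from the transplant should be fixed at or before the transplant. A cycle given afterwards can be received only by someone who has survived to receive it. If such cycles enter the count, the patient moves to a higher class because of having survived, and takes an early-death-absent record along. Patients who die soon after HSCT cannot move. High cycle counts then look safer, and a real harmful effect of exposure is diluted.

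Risk factors for early death of HSCT patients are a stated objective (Protocol 7.2). SAP 6.4 names the number of cycles as a potential risk factor for liver disorder and for VOD/SOS. An artificially reassuring ratio for this factor would therefore work against the purpose of the survey.

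**Working it through.** **The plan's own figure.** The documents give no number for this factor. The only calculated figure is the power for a VOD/SOS risk-factor comparison (Protocol 8.10.2). With overall incidence 12.3%, relative risk 3.0 and a 1:1 split, the low-risk rate is 2 × 12.3% / (1 + 3) = 6.15% and the high-risk rate is 18.45%. With 88 per group and a two-sided 0.1 pooled chi-square test, power is 80.4% (80.2% with the rounded 18.5% and 6.2%). The stated 80.4% reproduces, and this point does not affect it.

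**How neighbouring factors are anchored**

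| Factor | Anchor |
|---|---|
| Laboratory values and ECOG PS | Before drug start or before conditioning, e.g. "Myeloblast count before conditioning for the first HSCT after the start of this drug" |
| Best response (Protocol 8.8.11.1) | "the best overall response before the start of the subsequent treatment or HSCT, whichever is earlier, will be entered" |
| MRD (Protocol 8.8.11.2) | Same cut-off as response |
| Treatment cycles | None stated |
| "Time from the date of final dose of this drug to the date of the first HSCT after the start of this drug" | Lowest class is under 4 weeks; no class for a final dose after HSCT |

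A patient dosed after HSCT would thus have an inflated cycle count and no valid class for the last factor.

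**Illustration with counts (all inputs assumed).** Take 80 recipients, 15 with 4 or more cycles before HSCT and 65 with 3 or fewer. Early death is 20% in both groups: 3/15 and 13/65, a true ratio of 1.00. Let k patients alive at day 100 cross from the low to the high class through later cycles. Then

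RR = [3/(15 + k)] / [13/(65 − k)]

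- k = 0: (3/15)/(13/65) = 1.00
- k = 2: (3/17)/(13/63) = 0.86
- k = 5: (3/20)/(13/60) = 0.69
- k = 8: (3/23)/(13/57) = 0.57

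**The same check with proportions (assumed).** Let d be the 100-day death risk, h the share with 4 or more cycles before HSCT, and r the share of day-100 survivors in the low group who cross. The share moved is m = (1 − h)(1 − d)r, and

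RR = [hd/(h + m)] / [(1 − h)d/(1 − h − m)]

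For d = h = 0.20 and r = 5%: m = 0.80 × 0.80 × 0.05 = 0.032, so RR = (0.04/0.232)/(0.16/0.768) = 0.83.

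| r | RR at d = h = 0.20 | Range for d and h from 0.10 to 0.30 |
|---|---|---|
| 0 | 1.00 | 1.00 |
| 2% | 0.92 | 0.85–0.95 |
| 5% | 0.83 | 0.68–0.89 |
| 10% | 0.70 | 0.50–0.80 |

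**A real effect (assumed).** With early death 15% in the low group, 30% in the high group and h = 0.20, the true ratio is 2.0. At r = 5%, m = 0.80 × 0.85 × 0.05 = 0.034 and the observed ratio is (0.06/0.234)/(0.12/0.766) = 1.64. At r = 10% it is 1.37.

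**The case against.** The strongest reply is that the plan assumed dosing would end before HSCT. Protocol 8.2 has the number of cycles decided with the transplant schedule in view. The final-dose-to-HSCT classes and their histogram start at zero. Overall survival in HSCT recipients is also measured from the final dose (SAP 6.2). If dosing always ends first, the total count equals the pre-HSCT count and nothing is biased. This stands as a reading of intent, but it is written nowhere. The listing item on resumption shows that a restart was foreseen.

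A reader might infer that the factor does count cycles after HSCT, or that patients are known to resume after HSCT. The documents support neither. They are silent on which cycles count. Resumption is listed beside disease name and salvage line with no date relative to HSCT, and it also appears in the VOD/SOS listing, which is not restricted to transplant recipients. A category for two or more HSCTs after drug start (SAP 8.2.2) does not imply dosing between them.

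A reader might also carry the survivor argument over to VOD/SOS. That fails: cycles given after HSCT but before onset are real exposure and could contribute. Only cycles after onset cannot have caused the event. Dosing may also be withheld because of VOD/SOS, so the net direction is open.

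Sampling error is large as well. In the count illustration, the log-scale standard error at k = 5 is √(1/3 − 1/20 + 1/13 − 1/60) = 0.586, giving a 95% interval for 0.69 of about 0.22 to 2.2. At k = 8 the interval for 0.57 is about 0.18 to 1.8. SAP 4.1 treats p-values as descriptive, and the dosing and HSCT listings would let a careful reader see dosing after HSCT. These facts limit the harm to interpretation. They do not supply the missing definition.

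**Conclusion.** The point holds as a gap in definition, and it is minor. The cycle factor for early death has no cut-off at the transplant from which the outcome is counted, while laboratory, ECOG PS, response and MRD factors do have an anchor. If any recipient is dosed after HSCT and the total count is used, the risk ratio for many cycles is biased downward.

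The size cannot be derived from the documents. The ratios above rest on assumed numbers of recipients, death risks and crossings, and with no dosing after HSCT the effect is nil. They also take every patient who crosses as alive at day 100. That is certain for cycles started after day 100; for earlier cycles, only survival up to the dose is certain. In the two-class version, only patients who pass from 3 to 4 cycles matter.

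For VOD/SOS with HSCT, only the narrower statement holds: cycles started after onset should not be counted, and the direction of bias is not determined.

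**What to change.** - **SAP 8.2.3.3, with a matching note in 5.4:** define the factor as the number of cycles started before the first transplant that follows drug start. Compute the final-dose-to-HSCT interval from the last dose before that transplant, so that no negative interval can arise.
- **SAP 8.2.3.1, HSCT part:** exclude cycles started after VOD/SOS onset. Using the same pre-HSCT count achieves this.

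The cost is a sentence in each section and a date condition in the program, since dosing and transplant dates are already collected. The cycle factor is used for subgrouping only in these two analyses, and the descriptive totals in SAP 8.2.2 can stay as they are. For early death there is no analytic loss. For VOD/SOS the pre-HSCT count ignores any exposure between HSCT and onset; that small cost should be stated with the result.
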